The goal of this proposal study is to develop and test a model of CHW health coaching, designed to prevent the onset of Type 2 DM in a large population of underserved patients at risk. CHWs will be recruited from the target populations and trained in core competencies to serve as peer health coaches. Our central premise is that CHWs are uniquely suited to engage fellow patients by encouraging lifestyle change through shared experiences and social support to extend the reach of primary care (PC) beyond the clinic visit. This study will test a scalable model of peer health coaching to address the millions of patients at risk for DM, using low cost, culturally congruent personnel to promote prevention of DM in PCMH practice.

Background

Type 2 DM is a preventable chronic disease that affects 11% of US adults. An additional 35% (79 million) have pre-DM and thus at risk of developing DM and cardiovascular disease. DM is a leading cause of death in the US and a major cause of heart disease and stroke. It is essential that the US leverage prevention strategies to mitigate the health and economic impact of DM in the population. Up to 20% of adult PC patients at BH and 25% of veterans at NY Harbor have DM, 2x and 3x the rate in the general population, respectively, and this rate has been steadily increasing. There is also a substantial population with undiagnosed pre-DM, half of who are expected to develop DM in the next decade. Our preliminary analysis of VA NY Harbor data from 2010-2012 showed that 9,610 (62%) of 15,500 veterans <75 years old, without DM, had a glycosylated hemoglobin (HbA1c) test, and 1,730 (18%) of them had pre-DM.

Study Design

We will conduct a cluster-randomized trial to test the impact of peer health coaches on prediabetic patients cared for by PCMH teams at BHC and VA to:

1. Reduce the incidence of type 2 DM in pre-diabetic, PCMH patients;
2. Promote weight loss among pre-diabetic patients;
3. Increase patient activation levels, a measureable construct of engagement, efficacy, skills, and confidence in managing one's health, among pre-DM patients, resulting in:
 - a. Improved secondary clinical outcomes: better glycemic and blood pressure control, and lower Framingham risk scores;

- b. Increased utilization of preventive services (e.g. MOVE!, TeleMOVE!, Healthy Lifestyles, etc.);
- c. Improved health behaviors (e.g. making dietary and exercise changes); and

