- 4. Develop, implement and assess strategies to recruit, train, and integrate peer CHW health coaches within the PCMH model.

The 36-month intervention will be conducted using a staggered entry design across four, overlapping, 12-month waves to account for CHW caseload limits. This study will test a scalable model of peer health coaching to address the millions of patients at risk for DM, using low cost, culturally congruent personnel to promote prevention of DM in PCMH practice. If successful, our study team will work with VA's Central Office and NY City's Health and Hospital Corporation to translate the model for larger scale implementation.

Characteristics of the Research Population

Number of Subjects

All 12 PC teams at VA NY Harbor and all 4 PCMH teams at BH will be eligible to participate. In our VA PROVE study, 51/52 PCPs participated in the intervention, and we expect similar rates in this project. Eligible patients will be identified through the study's pre-DM registry, which will be based on the EMR and Corporate Data Warehouse (CDW) at each site. This methodology builds on our ongoing national, retrospective cohort study of predictors of DM among veterans with pre-DM back to 2008. Based on preliminary analysis of VA NYHHS data from 2010-2012, 62% of veterans enrolled in PC without DM, have had an HbA1c test in the previous two years.

In the intervention group, we anticipate contacting 2,100 randomly selected patients (1,050 at the VA* and 1,050 at BH) to ultimately enroll about 1,100 patients (550 at the VA and 550 at BH). This outreach sample reflects our assumption that 20% of patients will be unreachable and that 60% of those reached will enroll in the study. Another 1,100 patients attributed to control group providers will be randomly selected as the control group, in accordance with the waiver of HIPAA authorization. As detailed below, the control group will not participate in the CHW intervention. The total sample, including the intervention and control groups, will be about 2,200 patients. This amounts to approximately 265 patients (across intervention and control groups) per wave and per clinical site.

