Influence of neighborhood factors: To examine the influence of contextual factors on implementation and intervention effectiveness, we will conduct population-level analysis of variation in implementation and health outcomes across NYC neighborhoods. We will conduct this analysis with patient data available at the start of the study and data on enrolled patients post-intervention. To obtain information on neighborhood-level factors, we will use publically available data on social and environmental aspects of NYC neighborhoods in the FACETS database (data accessible at <https://github.com/mcantor2/FACETS>). We will map patient addresses to census tracts, aggregate census tracts to neighborhoods, and statistically examine the association of neighborhood-level contextual factors on prediabetes prevalence across NYC. Patients' location information will be used at an aggregate neighborhood level, and it will not be possible to identify their precise location in the city. Individual patients and their PHI will not be identifiable.

Data Analysis and Data Monitoring

The analytic methods described below are designed to test the primary hypotheses that prediabetic patients cared for by PCMH teams randomly allocated to the CHW Coaching group, will have lower annual hazard rate of incident cases of DM overtime more weight loss, and higher PAM scores by the end of the intervention

period than similar patients cared for by PCMH teams allocated to the Control group, adjusting for baseline rates. The unit of analysis is patients, aggregated to the provider level.

Analysis: Patient Clinical Outcomes and Health Behaviors

Descriptive analysis techniques (measures of central tendency and variability, frequencies and proportions) will be used to present baseline characteristics of participants (patients and their PC staff) in the control and intervention arms. Chi-square tests and t-tests will be used to check if these baseline characteristics are balanced between the two study groups. For continuous outcomes, normal assumptions will be checked, and non-parametric alternatives and transformations will be considered as needed.

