To assess the overall effectiveness of the CHW intervention we will compare cumulative DM incidence rates and time to DM incidence (in addition to other outcomes: weight loss, obesity rate, and health care utilization) between the two study groups, using intention-to-treat and per protocol analyses. Time to DM incidence at 12-month follow-up of the intervention and control arms, aggregated across the 4 study waves, will be compared using Cox proportional hazard regression models. Chi-square analyses will be conducted to compare outcomes between the two groups for categorical variables (e.g. obesity rate, PAM stage) and t-tests will be conducted for continuous outcomes (e.g. weight change, PAM score). We will then conduct (generalized) linear mixed-effects modeling, which will (1) take into account the intra-cluster correlation coefficient (ICC) of patients within providers and teams, (2) analyze repeated measures at several time-points (baseline, midpoint, and post-intervention) simultaneously, (3) include team or patient level baseline covariates easily, if they are found to be unbalanced between two arms, and (4) deal with attrition problems and other missing data automatically. For categorical outcomes, such analyses will be implemented using SAS Proc GLIMMIX, while using SAS Proc MIXED for continuous outcomes.

We will use multilevel survival analysis to determine the effect of the intervention on time to DM, as patients are enrolled in waves and the time to DM incidence may be censored by the end of study. Specifically, we will fit Cox proportional hazard regression models with mixed effects to examine the hazard ratio between two groups, adjusting for important covariates and taking into account the correlation among patients within teams.

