While the above inclusion and exclusion criteria return about 9,300 eligible patients, 8,200 at BH and 1,100 at the VA, CHW caseload limitations preclude us from reaching all these eligible patients during the 3-year intervention. Assuming a caseload of 72 patients per fulltime CHW per wave (with 3.5 fulltime equivalent CHWs across both sites and 4 waves), the intervention is projected to enroll a minimum of 1,008 subjects into the intervention group. An equivalent number of subjects will be randomly selected from the Control teams for a total of at least 2,016 study subjects overall. The intervention and control subjects will be split across the two study sites. After assuming that we will not be able to reach about 20% (due to missing or incorrect contact information) unreachable rate, and that about 60% will consent to enroll in the intervention, we will randomly select about double the 1,008 subjects (about 2,100) for potential enrollment into the intervention in order to enroll the minimum of 1,008 intervention subjects needed to have adequate statistical power.

Power: In the pre-DM population we estimate the 3-year DM incidence to be 15% (based on preliminary analysis of a similar VA cohort from 2010-2012). Based on our analyses, with 1,008 patients allocated to each of the intervention and control groups, we anticipate having 80% power ($\alpha = 0.05$) to detect a difference in time-to-event (DM incidence) between the intervention and control group.

To assess measures of implementation fidelity, specifically coverage, duration, and frequency of CHW-patient contact, we will base calculations on all patients enrolled. Since we will use all available study data from the electronic medical records, power and sample size considerations do not apply. We will assess content of CHW-patient contact using qualitative methods, hence power and sample size considerations do not apply.

To examine the variation in prediabetes prevalence across NYC neighborhoods, we will use available data from BH at the start of the study, in approximately 19,000 patients. These patients meet the study's previously stated eligibility criteria, with two modifications: patients must have (1) any HbA1c result in the past 5 years and (2) an address available in the EHR. Data on all enrolled BH patients at the end of the study, an estimated 1,000 patients, will also be used. Since we will use all available study data, power and sample size considerations do not apply.

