All primary care staff will be given information about the proposed research during regular staff meetings, email announcements and a study flyer and then asked to participate. Staff providing verbal consent to participate will be randomized (as part of their PACT team) to either work with a CHW or serve as controls. Staff who opt-out will not be randomized, although might still work on a team that is included in the study. For example, if one primary care provider in a team declines participation, the other providers and team members consent, the team will be randomized to a study arm. If that team is randomized to an intervention arm, the

CHW would only work with the patients of the consenting providers. We anticipate that we will be able to obtain sufficient numbers of staff consenting to participate, as in our previous panel management study only one PCP out of fifty-one declined, and a majority of staff reported that the interventions and CHW support were helpful. Lastly, as CHWs will be extending services and interventions that are a part of regular, evidence-based practice on behalf of patients' primary care physician, patients will not individually consent to receiving phone calls, mailings, or any other contact with the CHW. For surveys, which are research procedures specific to this study, consenting elements will be presented at the top of the survey. Primary care teams will pre-approve all lists of patients receiving interventions as well as approving the content of the CHW's intervention. Patients will have the right to opt out of receiving outreach at any time. All mail materials will include instructions on how to stop receiving mail from the CHW.

A waiver of authorization for both recruitment/identification purposes and for study procedures has been sought. We use the electronic medical record to generate a list of eligible participants, in order to approach them to screen for eligibility. Without the requested Waiver, screening could not be practically carried out and would adversely affect the scientific rigor of the study.

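### The mixed model for weight does not state how team-to-team variation in change is carried; if team and provider effects are time-constant intercepts, as the text most naturally reads, they cancel from the arm-by-time contrast and the test is anti-conservative whenever teams differ in change

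*Combined protocol and SAP*

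**What the plan says.** The Study Design section sets out the design: "We will conduct a cluster-randomized trial to test the impact of peer health coaches on prediabetic patients". The consent section gives the unit of randomisation: staff "will be randomized (as part of their PACT team) to either work with a CHW or serve as controls". Number of Subjects gives the supply of clusters: "All 12 PC teams at VA NY Harbor and all 4 PCMH teams at BH will be eligible to participate".

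The opening of Data Analysis and Data Monitoring lists, with the diabetes hazard, "more weight loss, and higher PAM scores by the end of the intervention" among the primary hypotheses. It adds that comparisons adjust for baseline and that patients are analysed with aggregation to provider level.

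The subsection on patient clinical outcomes and health behaviors gives two steps for weight. First comes a t-test on weight change, with no clustering adjustment stated. Then comes a linear mixed model in PROC MIXED, which will "take into account the intra-cluster correlation coefficient (ICC) of patients within providers and teams, (2) analyze repeated measures at several time-points". The time-points are baseline, midpoint and post-intervention, modelled together. Baseline covariates enter only if the arms are found to be unbalanced on them. The plan gives no list of random effects, no team-by-time or provider-by-time term, no robust standard error, no degrees-of-freedom method and no ICC value.

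**The concern.** When baseline is one of the modelled outcomes, the intervention effect on weight loss is the arm-by-time contrast: the difference between arms in change from baseline. A team effect that is the same at every visit adds equally to baseline and follow-up, so it drops out of that change. Such a model does allow for teams differing in average weight. It does not allow for teams differing in how much weight their patients lose, and that is the variation that matters when teams are randomised. The standard error would then be close to that of a trial randomising about 2,000 patients individually.

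At stake is a stated primary hypothesis. Ordinary differences between teams in weight trajectory could be reported as an effect of the coaches, with intervals that are too narrow. The same applies to any other continuous outcome modelled this way, such as HbA1c or blood pressure. A degrees-of-freedom correction alone would not help, because it cannot restore an omitted variance component.

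**Working it through.** **The plan's own figures.** The patient numbers reproduce: 72 × 3.5 × 4 = 1,008 per arm, and 1,008 / (0.8 × 0.6) = 2,100 approached. The only power statement, "we anticipate having 80% power ($\alpha = 0.05$) to detect a difference in time-to-event (DM incidence"), concerns time to diabetes and cannot be reproduced because no hazard ratio is given. There is no power figure for weight to check.

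**Inputs.** From the documents: 2 × 1,008 = 2,016 patients, at most 16 teams, three time-points, alpha 0.05. Assumed: a two-sided test, 8 teams per arm, complete data, and an ICC of change (ρ) from 0 to 0.05. Equal teams have 2,016 / 16 = 126 patients.

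**Step 1: does the intercept cancel?** Write weight as arm and time effects + team intercept + patient intercept + team-by-time effect (variance σ²u) + residual (variance σ²e). The team and patient intercepts vanish from follow-up minus baseline. With n patients and k teams per arm, the variance of the contrast is

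2σ²e × (2/n) + 2σ²u × (2/k).

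Check with 8 teams of 20 per arm (n = 160, k = 8):
- No team-by-time variance, σ²e = 1: √(2 × 2/160) = 0.158. A generalised least squares calculation gave 0.158 with team-intercept variance 0, 1 or 10.
- σ²u = 0.05, σ²e = 0.95: √(0.02375 + 0.025) = 0.221. The same calculation gave 0.221.

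The intercept therefore plays no part in this test; the team-by-time term does.

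**Step 2: false-positive rate when σ²u is omitted.** With ρ = σ²u/(σ²u + σ²e), the true variance exceeds the model's by DEFF = 1 + (126 − 1)ρ. The rate is 2 × [1 − Φ(1.96/√DEFF)]. At ρ = 0.01, DEFF = 2.25 and 1.96/1.5 = 1.307, giving 19.1%. The last three columns come from 4,000 simulated null trials per row.

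| ρ | DEFF | Formula | Intercept-only model | Patient-level t-test on change | t-test on team mean change, 14 df |
|---|---|---|---|---|---|
| 0 | 1.00 | 5.0% | 5.2% | 5.2% | 5.0% |
| 0.005 | 1.62 | 12.4% | 11.9% | 11.8% | 4.9% |
| 0.01 | 2.25 | 19.1% | 19.4% | 19.2% | 4.4% |
| 0.02 | 3.50 | 29.5% | 29.4% | 29.4% | 5.1% |
| 0.05 | 7.25 | 46.7% | 46.2% | 46.0% | 4.7% |

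**Step 3: unequal teams.** If the two sites contribute equally, there are 12 VA teams of 84 and 4 BH teams of 252. The size-weighted mean is (12 × 84² + 4 × 252²)/2,016 = 168, so DEFF = 1 + 167ρ. The formula gives 23.0% at ρ = 0.01 and 34.7% at 0.02. Simulation (2,000 runs) gave 21.4% and 34.4%, against 4.3% and 5.2% for team mean change.

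**Step 4: in kilograms.** With an assumed SD of 12-month change of 6 kg, the intercept-only standard error is 6 × √(2/1,008) = 0.27 kg whatever ρ is. At ρ = 0.01 the correct value is 0.27 × 1.5 = 0.40 kg.

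**The case against.** The strongest reply is that the intercept-only model is inferred. Allowing for the ICC is one item in a list of four features and not a specification; it is compatible with team-by-time effects. The reference to baseline adjustment could mean follow-up weight modelled with baseline as a covariate, where a team intercept does carry variation in change. Aggregation to provider level would also carry some of it. A reader might infer from the table that the plan's weight test has an inflated error rate as a matter of fact. The documents do not support that: the random effects are not written out, no ICC of change is given, and at ρ = 0 there is no inflation.

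That much stands, and it makes the finding conditional. It does not dispose of the point. The analysis subsection is the operative text; it lists baseline among the repeated outcomes and brings in baseline covariates only if they are unbalanced. Nested intercepts are the ordinary meaning of an ICC of patients within providers and teams. Provider aggregation sits one level below the randomised unit. The other stated weight analysis, the t-test, gives no protection.

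It is also fair to say that the reach is limited. Incident diabetes is the outcome used for power, and the analysis subsection groups weight loss with the other outcomes. The mixed Cox model for time to diabetes has no baseline value to cancel against and is stated to allow for correlation within teams.

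**Conclusion.** The concern holds in conditional form. On its natural reading, the plan's mixed model leaves team-to-team variation in change out of the weight-loss test, and the plan says nothing that would rule that reading out. The test would then be anti-conservative whenever teams differ in change: about 12% to 47% false positives for an ICC of change between 0.005 and 0.05, and 5% if it is zero. The first-step t-test behaves in the same way.

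The size rests on an assumed ICC, a two-sided test, all 16 eligible teams taking part and splitting 8 v 8, complete data, and a team's deviation in change being shared by its patients across all four waves; inflation would be smaller if that deviation varied from wave to wave. Two wider conclusions that a reader might draw are not supported: that inflation has been shown to exist, and that the diabetes-incidence analysis is compromised.

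**What to change.** In the subsection on patient clinical outcomes and health behaviors, state that:

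- the PROC MIXED models for weight and other repeated continuous outcomes include random team-by-time and provider-by-time effects as well as the intercepts;
- the 12-month arm-by-time contrast is tested against team-by-time variation, with degrees of freedom based on the number of teams (16 − 2 = 14 if all take part);
- this analysis replaces the unadjusted t-test as the basis for inference.

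A model of 12-month weight with baseline as covariate and random team and provider intercepts is a useful sensitivity analysis. It is not equivalent: it uses neither midpoint values nor patients without a 12-month weight. That matters here because weights come from routine visits and the plan relies on the joint model to use all observed data under missing at random.

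The cost is a few sentences and no new data. The downside is wider intervals. With the 6 kg SD and ρ = 0.01, the 95% half-width goes from 1.96 × 0.27 = 0.53 kg to 2.145 × 0.40 = 0.86 kg, which is the precision that the design would then actually have.

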*We will work closely with the staff of another research study being conducted at the VA that has similar eligibility criteria, resulting in dual-eligible patients. In order to avoid patients being enrolled in both studies, which could result in patient burden, both studies will work with a statistician to identify these dual-eligible patients and randomly assign them to one study only prior to patient outreach and recruitment. 75% of these dual-eligible patients will be allocated to our study and 25% will be allocated to the other study in accordance with both programs' statistical power needs. Since both studies are similar in scope (e.g., weight loss, increasing exercise), we do not anticipate patients enrolled in one study will receive greater health benefits than patients enrolled in the other study.

Gender of Subjects

Subjects of both genders are included in the study.

Age of Subjects

The minimum age of the subjects is 18 and the maximum age is 75.

Racial and Ethnic Origin

There are no enrollment restrictions based upon race or ethnic origin.

Inclusion Criteria

Inclusion criterion: Having at least one HbA1c result in the prediabetic range (5.7-6.5%) in the 2 years prior to the start date of the study wave. In order to communicate with CHWs, patients must also speak either English or Spanish.

Exclusion Criteria

A diagnosis of DM, based on ICD-9 and ICD-10 codes applied during ambulatory encounters in the 2 years prior to the study wave; treatment with DM medication other than metformin (e.g. insulin or oral agents); age greater than 75 years; or exclusion by patient's PCP due to contraindication for lifestyle intervention or CHW outreach.

Vulnerable Subjects

The protocol includes collecting data from BH and VA clinical providers whose participation is vital to the success of the study. There is no coercion to enroll these clinic staff subjects. All such subjects can opt out by notifying the study staff that they would no longer like to participate in the study. Alternatively, subjects can decide not to complete surveys.

As we will be surveying a large random sample of pre-diabetic patients, it is possible that some of the survey respondents will be pregnant, mentally disabled, economically or educationally disadvantaged. Their exclusion from possible participation would prevent us from accurately sampling the population at random.

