- *Telephone-Based Coaching:* CHWs will offer a minimum of 6 monthly, 30-minute phone counseling sessions to all patients using motivational interviewing (MINT) and brief action planning (BAP). However, patients will be offered more frequent coaching, up to once per week. BAP is a counseling approach emphasizing goal setting and MINT principles that can be completed in short telephone counseling sessions.

Telephone coaching will be timed to occur just before or after PC visits to optimize the value of the visit for DM prevention. For patients with lower activation scores (Stages 1 and 2), who are less engaged in their own care, CHWs will prepare patients for PC visits, empowering them to ask questions, seek information and participate in decision-making. This approach can increase PAM scores and help patients to have more effective

encounters with their health care teams and to improve health outcomes such as HbA1c among patients with chronic illnesses.

- CHWs will re-call patients, who are not yet ready to engage in behavior change during the initial phone call, every 6 months unless they ask to be taken off the re-call list.
- *Referral to VA's MOVE! Program or BH's Healthy Lifestyles Program*: These programs offer a series of weekly workshops (BH 8 weeks, VA 12 weeks) focused on healthy eating and exercise. Patients “graduate” after 6 months but then continue with maintenance activities and ongoing peer support. CHWs will also encourage VA patients to participate in Tele-MOVE!, which provides daily interaction with in-home messaging technologies, and clinician contact as needed.
- *Referral to the DM Prevention Program (DPP)*: The DPP is a 16-session, weekly lifestyle intervention with certified DPP coaches, which is effective in preventing DM onset in pre-diabetics. The intensive program is then followed by monthly maintenance phone workshops with the DPP coach. This program will be provided by the study to all patients who wish to participate. These programs are offered by the NYCYMCA and by other community-based organizations.
- *Metformin*: Although not commonly used for DM prevention, metformin has been shown to prevent DM among patients with pre-DM, particularly those struggling with making lifestyle changes or with a BMI > 30. CHWs will suggest that such patients with normal renal function (GFR > 50%) discuss this option with their PCP and will provide a list of these patients to the team.

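### Baseline covariates are chosen by balance tests in the mixed models and left unnamed in the Cox model; baseline HbA1c and baseline metformin use are pre-specified in neither

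*Combined protocol and SAP*

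**What the plan says.** The section Analysis: Patient Clinical Outcomes and Health Behaviors treats covariates differently in different models.

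- **Balance check.** "Chi-square tests and t-tests will be used to check if these baseline characteristics are balanced between the two study groups". No significance threshold is given and clustering is not mentioned.
- **Mixed models (GLIMMIX and MIXED).** Among their listed features is that they "include team or patient level baseline covariates easily, if they are found to be unbalanced between two arms". As written, these models cover categorical outcomes, which takes in cumulative diabetes incidence.
- **First Cox comparison.** Twelve-month time to diabetes, "aggregated across the 4 study waves, will be compared using Cox proportional hazard regression models". No covariates are mentioned.
- **Mixed-effects Cox model.** A separate paragraph describes it as "adjusting for important covariates and taking into account the correlation among patients within teams". It has no balance condition and no list.

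The statement of the primary hypotheses under Data Analysis and Data Monitoring adds "adjusting for baseline rates", which is not defined.

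Two baseline variables stand out. Inclusion Criteria requires: "Having at least one HbA1c result in the prediabetic range (5.7-6.5%) in the 2 years prior to the start date of the study wave". Exclusion Criteria removes patients on "treatment with DM medication other than metformin", so metformin users can enter. Under CHW Intervention, the metformin item says it is not in common use for this purpose but that "metformin has been shown to prevent DM among patients with pre-DM". Neither variable is named as a covariate in any model.

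**The concern.** Choosing covariates by a balance test ties the model to a result seen after the data are in. It uses the wrong criterion, because how strongly a variable predicts the outcome matters more than whether its arm difference reached significance. Here the test is also unreliable: at most 16 teams are randomised, and a patient-level chi-square or t-test treats their patients as independent. Two trials run in the same way could therefore fit different models.

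In the Cox model the problem differs. With no covariates named, several specifications remain open once outcomes are known. One of them would be harmful: adjusting for metformin started during follow-up. Community health workers are to prompt suitable patients to raise metformin with their physician, so later use lies on the pathway from intervention to outcome, and adjusting for it would remove part of the effect under study.

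At stake are a model fixed in advance for the outcome on which the trial is powered, and whatever precision baseline HbA1c can add.

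**Working it through.** **1. The plan's own figures.** Statistical Power and Sample Size gives 72 patients × 3.5 full-time equivalents × 4 waves = 1,008 per arm, and 2,100 × 0.80 × 0.60 = 1,008. Both reproduce. The stated 80% power does not, because no hazard ratio (HR), sidedness or ICC is given. Solving for the HR that gives 80% power, two-sided 5%, by the Schoenfeld formula and with no design effect: 0.707 over 3 years (control risk 15%, about 261 events), or 0.539 over 12 months (about 82 events). The 12-month control risk assumes a constant hazard: −ln(0.85)/3 = 0.0542 per year, so 1 − exp(−0.0542) = 5.3%.

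**2. How often the balance test flags chance imbalance.** Number of Subjects gives 12 + 4 = 16 teams. Assuming an even 8/8 split and equal sizes, 1,008/8 = 126 patients per team. The design effect is DE = 1 + 125 × ICC. A test nominally at 5% (threshold assumed) then flags with probability 2[1 − Φ(1.96/√DE)].

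| Assumed ICC of covariate | DE | 1.96/√DE | Flag rate |
|---|---|---|---|
| 0 | 1.00 | 1.960 | 5% |
| 0.01 | 2.25 | 1.307 | 19% |
| 0.02 | 3.50 | 1.048 | 29.5% |
| 0.03 | 4.75 | 0.899 | 37% |

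Simulation agrees: 18% at ICC 0.01, 27% to 30% at 0.02, and 36% to 37% at 0.03. Patients are to be divided about equally between sites while the VA has 12 teams and Bellevue 4, so real teams would be unequal. At a given ICC that raises the flag rate.

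**3. What the choice of rule costs.** Three rules were simulated, with 2,000 trials per scenario, 1,008 patients per arm, 16 equal teams and one standardised baseline covariate in an exponential proportional-hazards model. The documents give no association between any baseline variable and diabetes, so a covariate HR of 1.5 to 2.0 per SD is assumed. The last column is always minus if flagged.

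| Follow-up, true HR | Covariate HR per SD | ICC | Power: never / always / if flagged (%) | Gain (points) |
|---|---|---|---|---|
| 3 years, 0.70 | 1.5 | 0 | 79.2 / 79.8 / 79.2 | 0.6 |
| 3 years, 0.70 | 2.0 | 0 | 78.0 / 80.5 / 78.3 | 2.2 |
| 3 years, 0.70 | 1.5 | 0.02 | 80.0 / 80.7 / 80.0 | 0.7 |
| 3 years, 0.70 | 2.0 | 0.02 | 75.6 / 79.4 / 77.4 | 2.0 |
| 12 months, 0.56 | 1.5 | 0 | 71.8 / 71.9 / 71.8 | 0.1 |
| 12 months, 0.56 | 2.0 | 0 | 70.2 / 71.8 / 70.6 | 1.2 |
| 12 months, 0.56 | 1.5 | 0.02 | 73.8 / 74.0 / 73.8 | 0.2 |
| 12 months, 0.56 | 2.0 | 0.02 | 70.2 / 72.6 / 71.8 | 0.8 |

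The gain runs from 0.1 to 2.2 points. With Monte Carlo error of about 1 point, that is best read as about 0 to 2.5. Under no effect, type I error was 4.2% to 6.0% for the flag-based rule and 4.4% to 5.8% for fixed adjustment.

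The simulations put no residual team effect on the outcome, so the power values serve to compare the rules and do not forecast the trial's power.

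**The case against.** **The balance rule does not govern the Cox model.** This stands in full. A reader might infer that baseline HbA1c enters the time-to-diabetes model only if a test flags it, so that an imbalance just short of significance stays in the hazard ratio. The documents do not say so: the balance clause belongs to the mixed models, and the Cox paragraph has its own wording. What remains for the Cox model is that its covariates are unnamed. The phrase about baseline rates does not name them either, since patients with diagnosed diabetes are excluded and incident diabetes has no patient-level baseline rate.

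**The clause describes a capability.** It says what mixed models can do, never says only, and does not bar covariates chosen on other grounds. For outcomes measured repeatedly, such as weight or HbA1c, baseline is already a modelled time-point. This stands in part: no other basis for selection is offered for the mixed models, and the balance tests are planned in the paragraph just before. The plan also speaks of aggregating patients to provider level, but does not say that the balance tests use provider means.

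**The numerical cost is small.** This stands. A reader might infer a gain worth about 10% more events. In a second simulation at its strongest setting (hazard up 40% per 0.1% HbA1c, ICC 0.03), the SD of the log hazard ratio was 0.207 unadjusted and 0.197 adjusted, and (0.207/0.197)² = 1.10. That compares with never adjusting. Against adjusting if flagged (0.198), it is (0.198/0.197)² = 1.01. The accompanying fall in false positives from 5.9% to 4.6% is also measured against the unadjusted model, and with 1,500 runs (standard error about 0.6 points) neither rate is clearly different from 5%.

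**The metformin part is unquantified.** This stands. Baseline prevalence is not given, metformin was not simulated, and its availability for every patient is inferred from the medication exclusion.

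**Conclusion.** The point holds as a weakness of pre-specification with a modest statistical cost. The mixed models rest covariate choice on tests that ignore clustering and would flag chance imbalance in roughly 19% to 37% of trials at an assumed ICC of 0.01 to 0.03. The Cox model leaves its covariates open. Fixed adjustment is worth about 0 to 2.5 points of power over the flag-based rule, showed no loss in any scenario, and fixes the model before outcomes are seen.

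The size rests on assumed ICCs, covariate effects, a 5% threshold and equal teams. It covers chance imbalance only. Intervention patients are those reached who consent, while controls are drawn at random under a waiver; any difference arising from that is not measured here, and covariate adjustment could correct it only in part. The documents do not support a claim that the hazard ratio is biased by the balance rule or that type I error is materially inflated.

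**What to change.** Remove the balance tests as a way of selecting covariates; a descriptive baseline table can stay. State that the Cox models and the mixed models of diabetes incidence will always include, in both arms:

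- the most recent HbA1c before wave start, as a continuous term. Eligibility guarantees that every patient has one. It need not be the qualifying result and may lie outside the entry range, so the plan should say which value is used;
- metformin prescription at wave start, yes or no, at baseline only, with use during follow-up expressly kept out of the model.

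Keep the list short because there are only 16 teams. Say which Cox analysis is primary, since the first is written without covariates and the second with unnamed ones. Adjustment for site and a sensitivity analysis without baseline metformin users are optional and not needed for this point.

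The cost is analysis-plan wording and two model terms. No new data collection is needed, though completeness of baseline metformin records at both sites should be confirmed.
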